# VERSION HISTORY

Version	Approval Date	Significant Changes from Previous Version		
1.0	24 April 2023	Original Protocol Version		

# STUDY SYNOPSIS

Title	Systane Complete Preservative Free Lubricant Eye Drops	
Protocol Numbers	DEC262-I001	
Study Sponsor	Alcon Research LLC	
	[name]	
Study Design	Post-Market, multicenter, non-comparative, single arm, open-label, prospective	
	clinical study	
Study Duration	The overall study duration (first subject screened to last subject's final study visit) is	
	expected to be approximately 2 months.	
Study Centers	5 sites in the US and/or outside US, where the product is commercially available	
Objectives	The objective of this post-market clinical follow-up (PMCF) study is to assess the	
	performance and safety of Systane Complete Preservative Free (PF) Lubricant Eye	
	Drops in subjects experiencing dry eye symptoms.	
Number of Subjects	54 evaluable subjects	
	Investigators will be asked to enroll approximately 22% of subjects with aqueous	
	deficient dry eye (i.e., 12 subjects), 45% of subjects with evaporative dry eye (i.e.,	
	24 subjects), and 33% of subjects with mixed dry eye (i.e., 18 subjects) as per the Tear	
	Film and Ocular Surface Society (TFOS) Dry Eye Workshop (DEWS) II criteria for	
	Dry Eye Disease (DED) stratification.	
Main Inclusion /	Subjects will be eligible to participate in the study if all of the following conditions	
Exclusion Criteria	exist:	
	
 
Subject must be at least 18 years of age.
 
	
	2. Subject must be able to understand and sign an Institutional Review Board	
	(IRB)/Independent Ethics Committee (IEC) approved informed consent	
	form.	
	
 
Subject must be willing and able to attend all study visits as required per protocol.
 
	
	
 
Subject with mild to moderate dry eye (Impact of Dry Eye on Everyday Life
 
Symptom Bother [IDEEL SB] >16-64)
 
	
	
 
Subject must be willing to discontinue use of all habitual artificial tear supplements and use only the study device as directed for the entire study duration.
 
	
	6. Subject using cyclosporine or other topical dry eye medications must be on a stable dosing regimen for ≥60 days prior to enrollment.	
	Subjects will be excluded from participation in the study if any of the following conditions exist:	
	Has suffered any ocular injury to either eye in the past 3 months prior to screening	
	Has undergone any other ocular surgery (including intraocular surgery) within the past 6 months or has any ocular surgery planned during the study	
	3. Employee or family member of Investigators or Alcon	
	Currently enrolled in any clinical trial.	
	5. Use of any systemic medication known to cause dry eye (e.g., anti-histamine,	
	anti-depressants, anti-psychotics, benzodiazepines, etc.) for less than 1 month before the Screening visit. If subject was on a stable regimen for at least a month prior to the Screening visit, the dosing regimen must not have changed for the duration of their participation in this study. In addition, subjects who did not currently use any of these medications could not start a	
	regimen while participating in the study.	

Study Device	Systane Complete PF Lubricant Eye Drops
Comparator	N/A
Endpoints	Primary effectiveness endpoints:  • Dry eye questionnaire via IDEEL-SB at entry and at Visit 3
	Safety endpoints:      Biomicroscopy findings (include corneal staining)      Best corrected visual acuity (BCVA)      Adverse events (AEs)      Device deficiencies
Statistical Methods	Statistical analyses will be presented overall and by DED groups (aqueous deficient dry eye, evaporative dry eye, mixed dry eye).  There is no statistical hypothesis for the endpoints in this study. Appropriate descriptive statistics will be computed and presented for all categorical and continuous endpoints. A full description of statistical methods will be presented in the Statistical Analysis Plan.  • For categorical variables, the number and percentage of subjects/eyes within each category of interest will be presented.  • For continuous variables, the number of subjects/eyes with non-missing data, mean, standard deviation, range, median, minimum, and maximum will be presented.  • There will be no imputation for missing data.  All visual acuity results will be presented in logarithm of the minimum angle of resolution (logMAR) scale after applying appropriate transformations/conversions.

# **ABBREVIATIONS**

Abbreviation	Definition
ADE	Adverse device effect
AE	Adverse event
ATP	Artificial tear products
BCVA	Best corrected visual acuity
CFR	Code of Federal Regulations
CRF	Case report form
DED	Dry eye disease
DES	Dry eye symptoms
DEWS	Dry eye workshop
eCRF	Electronic case report form
EDC	Electronic data capture
EU	European Union
FAS	Full analysis set population
FDA	Food and Drug Administration
GCP	Good Clinical Practice
GPCMS	Global Product Complaint Management System
HIPAA	Health Insurance Portability and Accountability Act of 1996
ICF	Informed consent form
ICH	International Conference on Harmonization
IDEEL-SB	Impact of Dry Eye on Everyday Life - Symptom Bother
IEC	Independent Ethics Committee
IRB	Institutional Review Board
logMAR	Logarithm of the minimum angle of resolution
NaFl	Sodium fluorescein
PF	Preservative Free
PG-HPG	Propylene glycol-hydroxypropyl-guar
PHI	Protected Health Information
PI	Principal Investigator
PMCF	Post-market clinical follow-up
PP	Per-protocol population
SADE	Serious adverse device effect
SAE	Serious adverse event
SOP	Standard operating procedures
TFOS	Tear Film and Ocular Surface Society
US	United States

#### 2 Introduction / Background and Rationale

Dry eye disease (DED) is a common ocular disorder, which affects many individuals worldwide. The prevalence of DED with/without symptoms ranges from 5% to 50%; and based on signs alone, up to 75%.

DED is characterized by a loss of homeostasis of the tear film resulting in ocular symptoms of discomfort, irritation, and visual disturbance, all of which significantly impact the patients' social and occupational quality of life. Tear film insufficiency may be the result of inadequate aqueous tear production by the main and accessory lacrimal glands, excessive evaporation of the tears from the ocular surface, or a combination of both.

Common factors associated with DED include elder age, female gender, and the presence of autoimmune disease. DED is also reported in younger and pediatric populations. Other modifiable factors that can contribute to DED include the use of computers and digital devices, the use of heating, ventilation, and air conditioning systems, diet and lifestyle.

While management of DED depends on the severity of symptoms and signs, use of artificial tear products (ATPs) that replace or supplement the deficient natural tear film is the mainstay treatment option.

Systane Complete lubricant eye drops is a propylene glycol-hydroxypropyl-guar (PG-HPG) nanoemulsion, designed to replenish deficiencies in both the lipid and aqueous layers of the tear film.

Systane Complete has been evaluated in several pre-clinical and clinical studies. PG-HPG nanoemulsion lubricant eye drops have been shown to improve dry eye symptoms, enhance tear film stability, and lipid layer thickness; hence, they help to restore eye surface health and provide symptom relief in patients with DED, regardless of subtypes.

Systane Complete Preservative Free (PF) are eye drops formulated without preservatives.

This post-market clinical follow-up (PMCF) study aims to generate scientific evidence to address safety, performance, and clinical benefits of Systane Complete PF in subjects with DED.

# 3 STUDY DEVICE DESCRIPTION

Study device description is presented in Table 1.

Table 1. Study Device

Name	Systane Complete Preservative-Free
Formulation	Propylene glycol solution/drops
Unit dose strength	0.06 mg in 1 mL (0.6%)
Route of Administration	Ophthalmic
Supply Type	Open label participant packs; bottles:
Packaging and Labeling	1 in 1 CARTON; 10 mL in 1 BOTTLE, DROPPER
	2 in 1 CARTON; 10 mL in 1 BOTTLE, DROPPER
	Labeled as required per country requirement.
Storage Conditions	Store at room temperature

#### 4 Preparation/Handling/Storage/Accountability

The study device should be handled as per the instruction for use.

Subjects will be asked to return the study device at Visit 3. Sites will account for the return of the study device accordingly, and are expected to dispose/destroy the study device per the standard practice.

#### 5 STUDY OBJECTIVES

The objective of this PMCF study is to assess the performance and safety of Systane Complete PF Lubricant Eye Drops in subjects experiencing dry eye symptoms.

#### 6 STUDY DESIGN

# 6.1 Overview of Study Design

This is a post-market, multicenter, non-comparative, single arm, open-label, prospective clinical study.

The study will be conducted in the US and/or outside the US, where the product is commercially available, in clinical sites known to routinely manage patients with DED. The overall study duration (first subject screened to last subject's final study visit) is expected to be approximately 2 months.

Subjects will be enrolled into the study after signing the informed consent form (ICF).

Subjects who meet all of the inclusion criteria and none of the exclusion criteria will initiate

[figure not shown]
treatment with Systane Complete PF. On Day 1, eligible study participants will be asked to instill one drop of Systane Complete PF in each eye on-site (during the Screening/Baseline visit) and the subsequent drop only after 8 hours ( $\pm$  1 hour) at home. For the rest of the study duration (up to Visit 3), subjects will be asked to self-administer 1-2 drops in each eye; four times a day. The dose selected in this study is the dose approved for Systane Complete PF for the management of DED.

Subjects will participate in the study for approximately 30 days, with a phone call scheduled on Day  $15 \pm 2$  (Visit 2) and a follow-up visit scheduled on Day  $30 \pm 2$  (Visit 3). Subjects may have unscheduled visits if deemed necessary per the Investigator's judgment.

Subjects will be asked to complete patient questionnaires on Day 1 (Impact of Dry Eye on Everyday Life - Symptom Bother [IDEEL-SB] and at Visit 3 (IDEEL-SB). In addition, subjects will be instructed to document Systane Complete PF dosing information on a daily basis using a subject diary.

[figure not shown]
A summary of the study design is shown in Figure 1. Systane complete preservative-free dose regimen is shown in Figure 2. Study assessments are shown in the Schedule of Assessments (Table 4).

The study will enroll approximately 68 subjects with the objective of 54 subjects completing treatment with Systane Complete PF. Investigators will be asked to enroll approximately 22% of subjects with aqueous deficient dry eye (i.e., 15 subjects), 45% of subjects with evaporative dry eye (i.e., 31 subjects), and 33% of subjects with mixed dry eye (i.e., 22 subjects) as per the Tear Film and Ocular Surface Society (TFOS) Dry Eye Workshop (DEWS) II criteria for DED stratification.

Systane Complete Preservative-Free will be dispensed at Screening/Baseline visit. Subjects will be expected to attend one additional visit at Day 30 (±2days) after screening and a telephone call visit at Day 15 (±2days).

Figure 2. Systane Complete Preservative-Free Dose Regimen

[figure not shown]
# 6.2 Anticipated Duration of the Clinical Investigation

The anticipated duration of the clinical trial is approximately 2 months. The anticipated number of clinical sites is up to 5. This will result in an accrual rate of 6.8 subjects per site per month.

# **6.3** Effectiveness and Safety Endpoints

# 6.3.1 Primary Effectiveness Endpoint

• Dry eye questionnaire via IDEEL-SB at entry and at Visit 3

#### 6.3.3 Safety Endpoints

- Biomicroscopy findings (include corneal staining)
- Best corrected visual acuity (BCVA)
- Adverse events (AEs)
- Device deficiencies

### 6.4 Study Population

The study population consists of adult male and female subjects (≥18 years old) with mild to moderate dry eye disease. Subjects will be recruited from clinical sites within and/or outside of the US, where Systane Complete Preservative-Free is commercially available.

#### 6.4.1 Sample Size

The study will recruit 68 subjects with a target to complete 54 evaluable subjects.

With a sample size of 54, a two-sided 95% confidence interval for a single proportion will extend 0.060 from the observed proportion when the expected proportion is 0.0543 (AEs).

Table 2 presents the precision for various rates of categorical outcomes.

**Table 2.** Precision for Various Percentages

Comple Size	Precision (%) for Various Rates of Outcomes				
Sample Size	5%	10%	25%	50%	
54	5.81%	8.00%	11.55%	13.34%	

Precision calculated according to a simple asymptotic formula for a 2-sided 95% confidence interval for a proportion based on the normal approximation of the binomial distribution.

Investigators will be asked to enroll approximately 22% of subjects with aqueous deficient dry eye, 45% of subjects with evaporative dry eye, and 33% of subjects with mixed dry eye as per the TFOS DEWS II criteria.

#### 6.4.2 Subject Recruitment

Subjects will be recruited from the clinical practices of the participating Investigators and surrounding metropolitan areas. Additional advertisement is not expected to be required.

#### 6.4.3 Prior and Concomitant Therapy or Medications

#### **Concomitant Medications**

Targeted concomitant medications (see Section 7.3.2) must be recorded in source documents and on the appropriate electronic case report form (eCRF).

#### **Prohibited Concomitant Medications**

For subjects who meet all of the inclusion criteria and none of the exclusion criteria, the initiation of systemic medications known to cause dry eye (e.g., anti-histamine, anti-depressants, anti-psychotics, benzodiazepines, etc.) or known to treat dry eye (e.g., Restasis, Xiidra, Cequa) is not permitted during the study.

#### **Rescue Medicine**

Not applicable.

#### 6.4.4 Inclusion Criteria

Subjects will be eligible to participate in the study if **all** of the following conditions exist:

- 1. Subject must be at least 18 years of age.
- 2. Subject must be able to understand and sign an IRB/IEC approved informed consent form.
- 3. Subject must be willing and able to attend all study visits as required per protocol.
- 4. Subject with mild to moderate dry eye (IDEEL SB >16-64).
- 5. Subject must be willing to discontinue use of all habitual artificial tear supplements and use only the study device as directed for the entire study duration.
- 6. Subject using cyclosporine or other topical dry eye medications must be on a stable dosing regimen for ≥60 days prior to enrollment.

#### 6.4.5 Exclusion Criteria

Subjects will be excluded from participation in the study if any of the following conditions exist:

- 1. Has suffered any ocular injury to either eye in the past 3 months prior to screening
- 2. Has undergone any other ocular surgery (including intraocular surgery) within the past 6 months or has any ocular surgery planned during the study
- 3. Employee or family member of Investigators or Alcon
- 4. Currently enrolled in any clinical trial.
- 5. Use of any systemic medication known to cause dry eye (e.g., anti-histamine, anti-depressants, anti-psychotics, benzodiazepines, etc.) for less than 1 month before the Screening visit. If subject was on a stable regimen for at least a month prior to the Screening visit, the dosing regimen must not have changed for the duration of their participation in this study. In addition, subjects who did not currently use any of these medications could not start a regimen while participating in the study.

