#### 7.3.2 Medical History/Concomitant Medications

Fully document concomitant medications (taken within the past 30 days prior to the Screening/Baseline Visit) and Medical History (within 1 year prior to the Screening/Baseline

Visit) in the subject source documents (i.e., subject's chart). If the subject reports any condition in Table 3, the Investigator may ask for additional information at their discretion.

AEs are collected from the time of informed consent. Any preexisting medical conditions or signs/symptoms present in a subject prior to the start of the study (i.e., before informed consent is signed) are not considered AEs in the study and should be recorded in the Medical History section of the eCRF.

In the electronic data capture (EDC), only limited information regarding concomitant medications and medical history will be captured, as noted below.

- Medical History: Document all ocular history and targeted systemic history. In the EDC, there is a prepopulated dropdown field with items of interest that is consistent with Table 3.
- Concomitant medications: Document all ocular medications and targeted systemic medications used to treat conditions documented in Medical History and AEs.

**Table 3.** Targeted Medical History

Medical History	Definition	
Active Respiratory Infections	Principal respiratory viruses known to cause ocular disease in humans:  Adenovirus Influenza virus Respiratory syncytial virus Coronavirus Rhinovirus Human metapneumovirus	
Alcohol Abuse	Heavy drinking: current or past consumption of 4 or more servings of alcoholic beverages daily	
Atopic Disease	
 
Atopy
 
Atopic dermatitis
 
Urticaria
 
Angioedema
 
Asthma
 
Allergic rhinitis
 
	
Cancer	
 
Cancers (potentially metastatic to eye or orbit), e.g., breast and lung cancer for women, gastrointestinal cancer for men, etc.
 
Cancers on active chemo- or radiotherapy
 
	
Diabetes Mellitus	All Type I and II, some potential risk factors for retinopathy include:	
Headache	Confirmed diagnosis (regardless of frequency of attacks) of:	

Medical History	Definition
·	
 
Tension-type headache
 
Cluster headache
 
Headache with symptoms:
 
Systemic symptoms (e.g., fever, weight loss)
 
Neurologic symptoms/signs
 

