#### **8.2** Statistical Methods

This section is a summary of the planned statistical analyses. A Statistical Analysis Plan will be finalized prior to database lock and will include a more technical and detailed description of the statistical analyses described in this section.

Statistical analyses will be presented overall and by DED groups (aqueous deficient dry eye, evaporative dry eye, mixed dry eye).

There is no statistical hypothesis for the endpoints in this study. Appropriate descriptive statistics will be computed and presented for all categorical and continuous endpoints.

- For categorical variables, the number and percentage of subjects/eyes within each category of interest will be presented.
- For continuous variables, the number of subjects/eyes with non-missing data, mean, standard deviation, range, median, minimum, and maximum will be presented.
- There will be no imputation for missing data.

All visual acuity results will be presented in logarithm of the minimum angle of resolution (logMAR) scale after applying appropriate transformations/conversions.

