# 9.7 Anticipated Clinical Benefits and Risks

#### 9.7.1 Known Potential Risks

Systane Complete Preservative-Free may cause mild eye burning or irritation, itching or redness of the eyes, watery eyes, blurred vision, or unpleasant taste in the mouth. There may be a rare possibility of an allergic reaction, which could be severe.

Systane Complete must be stopped in the event of eye pain, changes in vision, continued redness or irritation of the eye, or if condition worsens or persists for more than 72 hours.

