#### 1.3.2. Study Population

The study population consists of adult male and female subjects (≥18 years) with mild to moderate DED. Subjects will be selected based on the inclusion criteria and exclusion criteria listed in Sections 6.4.4 and 6.4.5 of the protocol.

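### Protocol 9.7.1 names a possibly severe allergic reaction as a known risk, but no eligibility criterion addresses a known prior reaction to the product, so such a subject can be eligible and dosed

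*Protocol*

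**What the plan says.** **Risk.** Protocol 9.7.1 lists mild local effects and then adds: "There may be a rare possibility of an allergic reaction, which could be severe". It gives no rate and does not mention people who have reacted before.

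**Eligibility.** Protocol 6.4.5 begins "Subjects will be excluded from participation in the study if any of the following conditions exist" and gives five conditions: recent ocular injury, recent or planned ocular surgery, being an employee or family member, enrolment in another trial, and systemic drugs that cause dry eye. Protocol 6.4.4 gives six inclusion criteria. Only the fifth is about using the product, and it reads: "Subject must be willing to discontinue use of all habitual artificial tear supplements and use only the study device as directed for the entire study". The synopsis carries the same two lists. SAP 1.3.2 adds nothing of its own: "Subjects will be selected based on the inclusion criteria and exclusion criteria listed in Sections 6.4.4 and 6.4.5 of the protocol".

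**From eligibility to dosing.** Protocol 6.1 says of starting treatment: "Subjects who meet all of the inclusion criteria and none of the exclusion criteria will initiate". On the first dose it says: "On Day 1, eligible study participants will be asked to instill one drop of Systane Complete PF in each eye on-site". Screening, baseline and first dose all fall within Visit 1.

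**History.** Protocol 7.3.2 has medical history (1 year back) and concomitant medications (30 days back) documented in source. Table 3 includes atopic disease and a free-text ocular row. On follow-up questions it says: "If the subject reports any condition in Table 3, the Investigator may ask for additional information at their discretion".

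**The concern.** The protocol identifies a foreseeable harm that it says could be severe, yet its entry rule does not ask about the group in whom that harm is most predictable.

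The situation is plausible. The product is on the market where the study runs (6.1, 6.4). Subjects come largely from the investigators' own practices (6.4.2), and inclusion criterion 5 expects habitual users of artificial tears. Some candidates may already have used this product or a related one, so a prior reaction could be found by asking. After the first on-site drop, dosing is done at home, with a telephone call around Day 15 and the next scheduled clinic visit around Day 30.

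Subject protection is what is chiefly at stake. A secondary point is interpretation: safety is part of the study objective, and AEs are the only outcome named in the precision statement in 6.4.1. An event in a subject already known to react would count towards the reported AE frequency although screening could have avoided it.

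**Working it through.** The claim concerns an absence, so the main check is to read every place where a criterion could sit.

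1. **Inclusion criteria (6.4.4):** 0 of 6 address allergy, hypersensitivity or prior reaction. Criterion 5 asks only for willingness.
2. **Exclusion criteria (6.4.5):** 0 of 5 do. The list is numbered 1 to 5 without a gap and matches the synopsis, so nothing suggests that a criterion was blacked out.
3. **Catch-all criteria:** there is no exclusion based on investigator judgement or on label contraindications.
4. **Table 3 history:** atopic disease is recorded, but no text links the answer to eligibility. There is no specific item for reaction to eye drops or their ingredients, and the look-back is one year.
5. **Exit reasons (6.4.6):** physician decision is listed as a reason to discontinue participation, not as an entry criterion.
6. **SAP 4.1:** ineligibility is reported only as an inclusion criterion not met or an exclusion criterion met. An investigator who declines a known reactor has no criterion to cite.

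A subject with a known prior reaction who meets the other items, including willingness to use the drops, is therefore eligible as written, and 6.1 leads from eligibility to the on-site drop.

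**Size, for illustration.** No hypothesis is affected: "There is no statistical hypothesis for the endpoints in this study". The only yardstick in the documents is the planning AE proportion of 0.0543 with n = 54 (Protocol 6.4.1, SAP 8). The stated precision reproduces:

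- Half-width = 1.96 × √(0.0543 × 0.9457 / 54) = 0.060, as stated.
- Expected subjects with an AE at that rate: 0.0543 × 54 = 2.9, or 0.0543 × 68 = 3.7.

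Safety is analysed in the Full Analysis Set, meaning everyone given at least one dose (Protocol 8.1; SAP 2.1 and 6.3). The natural denominator is therefore up to about 68, not the 54 completers:

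- One event in 68 subjects: 1/68 = 1.5 percentage points, and 1.5/5.43 is about 27% of the planning rate.
- One event if only 54 were dosed: 1/54 = 1.9 percentage points, about 34% of the planning rate.

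SAP 6.3.1 summarises ocular TEAEs by eye and non-ocular TEAEs by subject, in separate tables. With 68 subjects and both eyes dosed there are 136 eyes. An ocular reaction in one eye would be 1/136 = 0.7 points, and in both eyes 2/136 = 1.5 points. These figures suppose that one event occurs. They do not estimate how likely that is.

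**The case against.** The strongest reply is that several things stand between a known reactor and the first drop. Consent must cover the known risks (section 13). The subject must be willing to use the product. All ocular history is documented (7.3.2). The exit list includes screen failure and physician decision, and the exit form can be completed at Visit 1 (Table 4). The investigator is responsible for safe care (9.5). The product is also marketed, is handled according to its instructions for use (section 4), and has a package insert that goes to the ethics committee (section 13). That label is not available here and may already warn such users.

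Much of this stands. A reader might infer that a known reactor would certainly be dosed; the documents do not support that, because any of these steps could stop it. They are discretionary or indirect, however, and none is a condition of entry. What holds is that such a subject can be dosed under the rule as written.

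A reader might also infer that 9.7.1 and 6.4.5 contradict each other. They do not. The risk section states no contraindication for prior reactors, so this is a gap between two sections.

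Finally, it can be said that the effect on AE interpretation is speculative: no frequency is given, and events are listed and assessed for causality, so such a case would be visible. That is fair, and the point does not rest on bias.

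**Conclusion.** The point holds as a gap in the entry rule. A rare but possibly severe allergic reaction is a stated risk, none of the eleven criteria addresses a known prior reaction, and eligible subjects begin treatment at the same visit.

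The weight is on subject safety. The number of subjects affected cannot be estimated from the documents and is likely low. One event would be about 1.5 percentage points of a fully enrolled Full Analysis Set (1.9 if only 54 were dosed). It would be wrong to read this as a material distortion of a planned AE rate: the 5.43% is only a precision input, and the SAP defines no pooled subject-level AE rate to compare with it, since ocular events are counted by eye.

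The conclusion assumes that the eligibility lists are complete as published and that no unseen label text is meant to act as an entry criterion. It is worth correcting because the possible consequence is serious and the correction is small.

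**What to change.** The sponsor should reconcile 6.4.4, 6.4.5 and the matching synopsis lists with 9.7.1, so that the eligibility section states how a known prior reaction to the study device or its components is handled before the on-site Day 1 drop. The exact criterion is for the sponsor to set. If the sponsor considers that the product label already covers this, the eligibility section should say so and refer to it.

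SAP 1.3.2 refers back to the protocol lists, so its text need not change. Any such screen failure would then have a criterion to be reported under in SAP 4.1. The cost is about one line in 6.4.4 or 6.4.5 and one in the synopsis, and possibly a very few more screen failures.
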